13.2.2. Sample Size Calculations

Sample size calculations were performed in SAS software (SAS Institute Inc., Cary, NC, USA). A sample size is determined such that the non-inferiority of the primary objective is demonstrated that results are not appreciably worse in XPEDE arm compared to MENDEC Spine arm. Based on this information the assumptions for the sample size are:

- The Angulation is assumed to be approximately normally distributed.
- The Angulation is to be assessed at 24 weeks (6 months) after the procedure.
- The Angulation at 24 weeks (6 months) is expected to be 1.2 in the MENDEC Spine treatment, and 1.2 or more in the XPEDE. A difference in Angulation of 2.5 or less is considered clinically unimportant for this comparison (half standard deviation rule). It is considered the maximum acceptable increase in Angulation compared to the MENDEC Spine arm. Standard deviation of 5.0 at 1 month from CAFÉ study was conservatively used to derive the non-inferiority margin of 2.5.
- The standard deviation of the Angulation is expected to be approximately 5.6 for both arms. Standard deviation of 5.6 at 12 months from CAFÉ study was conservatively used as the standard deviation for both arms.
- The sample size should be sufficient to produce an 80% chance (power) of a significant result at a one-sided 0.025 significance level.

The non-inferiority margin "m" that characterizes the largest absolute difference considered to be dismissible is defined as 2.5. Since smaller values of Angulation are better, the hypotheses are based on lower-tailed test:

$$H_0: \mu_X(t) \geq \mu_M(t) + m \quad \text{vs} \quad H_A: \mu_X(t) < \mu_M(t) + m$$

Where: t is 24 weeks (6 months), μ_X is the mean of index VBA I in the XPEDE arm, μ_M is the mean of index VBA in the MENDEC and "m" is the non-inferiority margin.

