The analysis on the second primary endpoint based on Index Vertebral Body Angles will use multiple data points per patient according to the number of levels treated. Assuming not completely independence among measures within same patient the analysis will be performed by means of Generalized Estimating Equation (or mixed models for repeated measures) using patient as the subject. The model will have the Index Vertebral Body Angles as dependent variables and baseline value, number of level treated (as the multiple data points) and arm as explanatory variables. All assumptions for regression models will be assessed by viewing plots of the residual values. It will be claimed that XPEDE is not inferior to MENDEC with respect to Angulation if the upper bound of the two-sided 95% confidence interval of the difference ($\mu_X(t) - \mu_M(t)$) is less than the margin.

The overall study is considered reached if both the null NI hypotheses are rejected. A separate Statistical Analysis Plan (SAP) will be developed prior to data being analyzed to further describe statistical methods, pre-specified data handling rules, and pre-specified analyses that will be included in the final study reports. Any deviation from the pre-specified statistical analyses will be noted in the study report.

The Statistical Analysis Plan will include a comprehensive description of the statistical methods and analyses to be included in reports that include analysis of endpoints. Any change to the data analysis methods described in the CIP will require an amendment only if it changes a principal feature of the CIP. Any other change to the data analysis methods described in the CIP, and the justification for making the change, will be described in the clinical study report.

14. Ethics

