6.2. Primary Endpoint on Vertebral Body Angles

The following assumptions were used for the determination of the sample size for VBA non-inferiority hypothesis:

- The Angulation is assumed to be approximately normally distributed.
- The Angulation is to be assessed at 24 weeks (6 months) after the procedure.
- The Angulation at 24 weeks (6 months) is expected to be 1.2 in the MENDEC Spine treatment, and 1.2 or more in the XPEDE. A difference in Angulation of 2.5 or less is considered clinically unimportant for this comparison (half standard deviation rule). It is considered the maximum acceptable increase in Angulation compared to the MENDEC Spine arm. Standard deviation of 5.0 at 1 month from CAFÉ study was conservatively used to derive the non-inferiority margin of 2.5.
- The standard deviation of the Angulation is expected to be approximately 5.6 for both arms. Standard deviation of 5.6 at 12 months from CAFÉ study³ was conservatively used as the standard deviation for both arms.
- The sample size should be sufficient to produce an 80% chance (power) of a significant result at a one-sided 0.025 significance level.

The non-inferiority hypothesis on the Vertebral Body Augmentation assuming 20% of potential loss-to-follow-up, the total sample size for the study will be 148 randomized subjects by 1:1 randomization schedule. Since there are strata, the sample size should be 162 to be divisible of 18 strata, i.e. 81 patients per arm.

Since final sample size was determined to be 180 patients, i.e. 90 patients per arm.

7. Statistical Methods

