7.9.1.2. Primary Endpoint on Vertebral Body Angles

The primary endpoint on Vertebral Body Angles (VBA) is the mean change of Index Vertebral Body Angles from baseline at 6 months in the subjects treated with Kyphon®Xpede™Bone Cement compared with subjects treated with Mendec Spine Bone Cement. It will be claimed that XPEDE is not inferior to MENDEC with respect to Vertebral Body Angles if the upper bound of the two-sided 95% confidence interval of the difference (Mean Vertebral Body Angles in the XPEDE arm at 6 months - Mean Vertebral Body Angles in the MENDEC arm at 6 months) < 2.5.

X-ray images will be reviewed by independent radiological reviewers who will be blinded to the subjects' treatment groups for each analysis. Adjudications provided both by the site and by the independent reviewers will be analyzed separately. Final conclusion will be made according to independent reviewer adjudication.

The analysis will be performed by means of Generalized Estimating Equation (or mixed models for repeated measures) using patient as the subject. The model will have the Index Vertebral Body Angles as dependent variables and baseline value, number of levels treated (as the multiple data points), type of procedure and arm as explanatory variables. All assumptions for regression models will be assessed by viewing plots of the residual values.

As sensitivity analysis, comparison will be also performed by t-test on:

1. the average value of VBA for the 3 separate treated levels;
2. the value of VBA for all the 3 pooled treated levels.

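### The pooled-level sensitivity t-test for vertebral body angle ignores within-patient clustering, so its interval is too narrow if levels within a patient are positively correlated; the primary analysis is unaffected.

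*SAP*

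**What the plan says.** SAP 7.9.1.2 sets the main analysis of the angle endpoint: "The analysis will be performed by means of Generalized Estimating Equation (or mixed models for repeated measures) using patient as the subject". Protocol 13.4 specifies the same kind of model and gives the reason: "Assuming not completely independence among measures within same patient".

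SAP 7.9.1.2 then continues: "As sensitivity analysis, comparison will be also performed by t-test on" two quantities. The first is an average over the treated levels. The second is "the value of VBA for all the 3 pooled treated levels". No clustering correction is given for either t-test. The SAP does not say how the t-test results will be used, or that their intervals will be compared with the 2.5 margin. Neither document gives a within-patient correlation for the angle.

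**The concern.** A patient may have one to three treated levels. On its most natural reading, the second t-test takes each level as a separate observation. A two-sample t-test assumes independent observations, so this analysis drops the feature that protocol 13.4 uses to justify the primary model.

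If levels within a patient are positively correlated, the standard error is too small and the interval too narrow. In a non-inferiority trial that error favours the new product. A sensitivity analysis of a co-primary endpoint will be read as evidence on whether the primary conclusion is robust, so its error bars should be right.

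**Working it through.** **Inputs**
- Margin: protocol 13.2.2, "largest absolute difference considered to be dismissible is defined as 2.5".
- SD: SAP 6.2, "The standard deviation of the Angulation is expected to be approximately 5.6 for both arms".
- True difference 0: SAP 6.2, "expected to be 1.2 in the MENDEC Spine treatment, and 1.2 or more in the XPEDE", taken at equality.
- Error and power: SAP 6.2, "The sample size should be sufficient to produce an 80% chance (power) of a significant result at a one-sided 0.025 significance level".
- Levels per patient: 72% one, 21% two, 7% three (protocol 12 and 13.2.2, SAP 6.1).
- Planned size: about 243 levels in 180 patients; 20% loss for the angle endpoint (protocol 13.2.2).
- ICC: not in the documents. Assumed range 0 to 0.7.

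**1. The plan's own figure.** By the normal approximation, n per arm = 2 × 5.6² × (1.96 + 0.842)² / 2.5² = 78.8, so 79 per arm or 158 levels. The noncentral t version gives 80 per arm (power 0.801), or 160 levels, as stated. Then 160 / 0.80 = 200 levels and 200 / 1.35 = 148 patients, also as stated.

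**2. Design effect of the pooled level mean.** For unequal cluster sizes m, Deff = 1 + ICC × (E[m²]/E[m] − 1).
- E[m] = 0.72×1 + 0.21×2 + 0.07×3 = 1.35
- E[m²] = 0.72×1 + 0.21×4 + 0.07×9 = 2.19
- Deff = 1 + ICC × (2.19/1.35 − 1) = 1 + 0.622 × ICC

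**3. Effect on the interval and the error.** The naive width is 1/√Deff of the correct width. If the interval is read against 2.5, the one-sided error at the margin is Φ(−1.96/√Deff).

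| ICC | Deff | naive / correct width | coverage of nominal 95% CI | one-sided error |
|---|---|---|---|---|
| 0 | 1.000 | 1.000 | 95.0% | 2.5% |
| 0.1 | 1.062 | 0.970 | 94.3% | 2.9% |
| 0.3 | 1.187 | 0.918 | 92.8% | 3.6% |
| 0.5 | 1.311 | 0.873 | 91.3% | 4.3% |
| 0.7 | 1.436 | 0.835 | 89.8% | 5.1% |

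**4. In degrees.** 243 × 0.80 = 194 evaluable levels. Naive half-width = 1.96 × 5.6 × √(4/194) = 1.57. Multiplied by √Deff, it is 1.72 at ICC 0.3 and 1.80 at ICC 0.5, so the shortfall is 0.15 to 0.23.

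**5. Simulation.** With 72 completers and 97 levels per arm, SD 5.6, true difference 2.5 and 40,000 runs per ICC, the naive t-test had one-sided error 2.5%, 2.9%, 3.6%, 4.4% and 5.2% at ICC 0, 0.1, 0.3, 0.5 and 0.7. A patient-clustered standard error gave 2.5–2.7%. A t-test on one mean per patient gave 2.4–2.6%.

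**6. Allowing for stratified randomisation.** All levels of one patient lie in the same stratum (site, number of levels, procedure). Correlation that comes from those factors is largely balanced between arms. In a simulation with 180 patients, blocks of 2 or 4, 20% loss and 8,000 runs per case, the error at total ICC 0.3 was 3.7% if procedure explained none of the correlation, 3.1% if one third, 2.8% if half and 2.5% if two thirds. At total ICC 0.5 it was 3.9% with one fifth explained and 3.1% with two fifths. These splits are assumptions.

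**The case against.** The strongest objection is that no trial decision depends on this t-test. The success rule in SAP 7.9.1 and protocol 13.4 rests on the co-primary analyses, and the angle model clusters by patient. A reader might infer that the non-inferiority test itself, or the trial's type I error, is inflated. The documents do not support that: the pooled t-test is labelled a sensitivity analysis and is given no power to override the model. This stands in full.

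The size is also open. No ICC is given, and the table in step 3 applies to residual, within-stratum correlation. Step 6 shows the inflation shrinking, and in one case vanishing, when procedure accounts for much of the total. It is moderate in any case because 72% of patients contribute one level. This stands as a limit on the size, not on the direction, provided the residual correlation is positive.

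A reader might also infer that this t-test will look more favourable than the primary model. That is not shown. The primary model adjusts for baseline and procedure and the t-test does not; losing that adjustment tends to widen the interval while ignoring clustering narrows it. The net effect depends on a baseline correlation that the documents do not give.

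Finally, it is tempting to say that the first t-test already provides a sound patient-level check. Its wording could mean one mean per patient, or separate tests level by level, so it cannot be relied on as it stands.

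None of this makes the pooled standard error right. It contradicts the plan's own statement about dependence.

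**Conclusion.** The point holds in a limited form. As written, the pooled-level t-test has a standard error that assumes independence which the protocol disclaims. For positive residual within-patient correlation its interval is too narrow, by about 8% at ICC 0.3 and 13% at ICC 0.5. The corresponding one-sided error is about 3.6% and 4.3% if the interval is read against 2.5, a criterion that SAP 7.9.1.2 states for the endpoint but not specifically for this t-test.

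These figures rest on the planned 72/21/7% split of levels and on an assumed ICC; at ICC 0 there is no inflation, and stratification can reduce it. The fault lies in the standard error of one supplementary analysis. The primary conclusion, the success decision and the trial's type I error are unaffected. The consequence is that this analysis is weak support for the primary result.

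**What to change.** Change the sensitivity analyses in SAP 7.9.1.2 in one of two ways:
- keep the pooled-level comparison, but compute its interval with patient-clustered (robust) standard errors; or
- drop the pooled-level t-test and state that the first analysis is a t-test on one mean angle value per patient.

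Either change brought the simulated error back to about 2.5%. If both t-tests are kept, the first still needs that definition. The cost is one SAP line and a slightly wider interval; no new data, visits or patients are needed.

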7.9.2. Secondary Endpoints

The secondary endpoints include:

- Change of NRS score from baseline at 1 day and 3-month visit
- Change of ODI (see section 10.3 for details) from baseline at 1 day, 3-month visit and 6-month visit
- Change of SF-36 (see section 10.3 for details) from baseline at 1 day, 3-month visit and 6-month visit
- Change of Vertebral body height restoration (see section 10.3 for calculation) at 1 day and 3-month visit and 6-month visit
- Change of Vertebral body angle from baseline at 1 day, 3-month visit and 6-month visit

The analysis will use multiple data points per patient (1 day, 3 months, 6 months). Assuming not completely independence among measures within same patient the analysis will be performed by means of Generalized Estimating Equation (or mixed models for repeated measures) using patient as the subject ID. The model will have the NRS, ODI, SF-36 (PCS, MCS), height restoration and angle as dependent variables (for each model) and baseline value, arm as explanatory variables. All assumptions for regression models will be assessed by viewing plots of the residual values. Potential confounders could be included in the model to adjust estimates.

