5.2.2. Secondary Endpoints(s)

The secondary endpoints include:

- Change of NRS score from baseline at 1 day and 3 months
- Change of ODI from baseline at 1 day, 3-month visit and 6-month visit.
- Change of SF-36 from baseline at 1 day, 3-month visit and 6-month visit
- Change in Vertebral body height restoration at 1 day and 3-month visit and 6 month
- Change in Vertebral body Angles from baseline at 1 day, 3-month visit
- Adverse event through 6-month visit, in particular, the following events will be reported:

- Bone Cement Implantation Syndrome;
- Bone Cement leakage;
- Vertebral body compression fracture;
- Adjacent vertebral body fracture;

6. Study Design

The Xpede Study is a prospective, 1: 1 randomized, single blinded, multi-center human clinical trial designed to confirm the safety and efficacy profile of the Kyphon®Xpede™ Bone Cement for regulatory approval in China. This study will enroll up to 180 subjects in order to demonstrate that the Kyphon®Xpede™ Bone Cement is non-inferior to the Mendec Bone Cement by more than a small pre-specified amount in terms of the primary endpoint. This amount is defined as the non-inferiority margin (section 13 for details). Subjects will be randomly assigned with a 1:1 ratio to the Kyphon®Xpede™ Bone Cement arm or to the Mendec Bone Cement arm and then followed for a duration of 6 months in all sites. All study sites will be in China. All study sites and Investigators are provided under a separate cover.

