4.2. Secondary Objectives and Endpoints

The secondary endpoints include:

- Change of NRS score from baseline at 1 day and 3-month visit
- Change of ODI from baseline at 1 day, 3-month visit and 6-month visit
- Change of SF-36 from baseline at 1 day, 3-month visit and 6-month visit
- Change of Vertebral body height restoration at 1 day and 3-month visit and 6-month visit
- Change of Vertebral body Angles from baseline at 1 day, 3-month visit and 6-month visit
- Adverse events through 6-month visit. In particular, the following events will be reported:
 - Bone Cement Implantation Syndrome;
 - Bone Cement leakage;
 - Vertebral body compression fracture;
 - Adjacent vertebral body fracture;

5. Investigation Plan

The Xpede Study is a prospective, 1: 1 randomized, single blinded, multi-center human clinical trial designed to confirm the safety and efficacy profile of the Kyphon®Xpede™Bone Cement for regulatory approval in China. This study will enroll up to 180 subjects in order to demonstrate that the Kyphon®Xpede™ Bone Cement is non-inferior to the Mendec Bone Cement by more than a small pre-specified amount in terms of the primary endpoint. This amount is defined as the noninferiority margin (see section 13 from Protocol for details). Subjects will be randomly assigned with a 1:1 ratio to the Kyphon®Xpede™ Bone Cement arm or to the Mendec Bone Cement arm and then followed for a duration of 6 months in all sites. All study sites will be in China. Total duration of the study is anticipated to be approximately 12 months (6 months of enrollments and 6 months follow-up after study procedure).

Patients will be randomized 1:1 to either Xpede™ Bone Cement or Mendec bone cement. The sequence of treatments will be randomly permuted in blocks of 2 or 4 patients per block. The

Xpede Clinical Study

Statistical Analysis Plan

Version 1.0

Page 6 of 19

Medtronic

blocked randomization will be centralized and schedules will be created by the study statistician using statistical software. To minimize the selection bias, the randomization procedure for this study will use the site (3 sites), the number of vertebral to be treated (1,2 or 3) and the type of procedure (2 procedure: VP and BKP) as stratification factors, so that there will be a separate permuted block randomization list for each stratum (18). This guarantees treatment balance within strata.

[figure not shown]

Figure 1: Study Flowchart

6. Determination of Sample Size

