10.3.3. ODI

The Oswestry Disability Index (ODI) is one of the condition-specific questionnaires recommended for use with patients with back pain. It is composed by 10 section as follow:

Section 1: Pain Intensity

- I have no pain at the moment. [0 points]
- The pain is very mild at the moment. [1 point]
- The pain is moderate at the moment. [2 points]
- The pain is fairly severe at the moment. [3 points]
- The pain is very severe at the moment. [4 points]
- The pain is the worst imaginable at the moment. [5 points]

Section 2: Personal Care

- I can look after myself normally without causing extra pain. [0 points]
- I can look after myself normally but it is very painful. [1 point]
- It is painful to look after myself and I am slow and careful. [2 points]
- I need some help but manage most of my personal care. [3 points]
- I need help every day in most aspects of self care. [4 points]
- I do not get dressed, wash with difficulty and stay in bed. [5 points]

Section 3: Lifting

- I can lift heavy weights without extra pain. [0 points]
- I can lift heavy weights but it gives extra pain. [1 point]
- Pain prevents me from lifting heavy weights off the floor but I can manage if they are conveniently positioned, e.g. on a table. [2 points]
- Pain prevents me from lifting heavy weights but I can manage light to medium weights if they are conveniently positioned. [3 points]
- I can lift only very light weights. [4 points]
- I cannot lift or carry anything at all. [5 points]

Section 4: Walking

- Pain does not prevent me walking any distance. [0 points]
- Pain prevents me walking more than one mile. [1 point]
- Pain prevents me walking more than a quarter of a mile. [2 points]

Xpede Clinical Study

Statistical Analysis Plan

- Pain prevents me walking more than 100 yards. [3 points]
- I can only walk using a stick or crutches. [4 points]
- I am in bed most of the time and have to crawl to the toilet. [5 points]

Section 5: Sitting

- I can sit in any chair as long as I like. [0 points]
- I can sit in my favourite chair as long as I like. [1 point]
- Pain prevents me from sitting for more than 1 hour. [2 points]
- Pain prevents me from sitting for more than half an hour. [3 points]
- Pain prevents me from sitting for more than 10 minutes. [4 points]
- Pain prevents me from sitting at all. [5 points]

Section 6: Standing

- I can stand as long as I want without extra pain. [0 points]
- I can stand as long as I want but it gives me extra pain. [1 point]

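### The continuous secondary endpoints are defined visit by visit, but the model named in SAP 7.9.2 lists no visit or arm-by-visit term, so as written it gives one visit-averaged difference

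*SAP*

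**What the plan says.** SAP 4.2 and 7.9.2 and Protocol 5.2.2 all set out the continuous secondary endpoints by visit. For ODI the SAP has "Change of ODI from baseline at 1 day, 3-month visit and 6-month visit". For SF-36 the protocol has "Change of SF-36 from baseline at 1 day, 3-month visit and 6-month visit". Height is listed at the same three visits. NRS is narrower, "Change of NRS score from baseline at 1 day and 3-month visit", because the 6-month value is primary. Angle at 6 months is secondary in the SAP but not in Protocol 5.2.2, where it is only primary.

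For the analysis, SAP 7.9.2 states "The analysis will use multiple data points per patient (1 day, 3 months, 6 months" and names a "Generalized Estimating Equation (or mixed models for repeated measures) using patient as the subject ID". The outcomes enter "as dependent variables (for each model) and baseline value, arm as explanatory variables". The section allows unspecified confounders to be added and does not name visit among them. Neither document lists a visit or arm-by-visit term for these outcomes.

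Two other passages bear on the point. SAP 7.2 and Protocol 13.4 give a general rule, t-test or Mann-Whitney, for continuous comparisons between groups. SAP 7.9.1.2, for the primary angle endpoint, does list its repeat index (number of levels treated) among the explanatory variables.

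**The concern.** The endpoints ask up to three questions per outcome, one for each visit. The named model has one arm coefficient, so it can return only one answer, averaged over visits. For NRS the average also includes the 6-month value, which belongs to the primary endpoint.

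Three things follow if the model is run as written. A difference confined to one visit is diluted. An early and a late difference in opposite directions can offset each other and look like no difference. And because nothing in the model accounts for the general course of recovery, an arm that loses more patients at late visits contributes relatively more early, worse values. That gap in follow-up then shows up as an arm effect.

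**Working it through.** **Inputs from the documents.** NRS margin 1.5, SD 3.27, 90 patients per arm (SAP 6.1). The model terms come from SAP 7.9.2. No sample size or power is stated for the secondary analyses. As a check on the inputs, the primary NRS figure reproduces: 76 per arm gives power 0.802 by the noncentral t, so 152 in total, and 152/0.85 = 178.8, or 179.

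**Assumptions.** The patterns of difference over visits, the visit means and the within-patient correlations are not in the documents.

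**Step 1: what the arm coefficient estimates.** Arm and baseline do not vary within a patient. With complete data, and an independence or exchangeable correlation structure, the coefficient is therefore

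(d1 + d3 + d6)/3,

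where d1, d3 and d6 are the arm differences at 1 day, 3 months and 6 months. The SAP names no correlation structure. Another choice would change the weights but would still give one number.

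**Step 2: numbers on the NRS scale.** Simulated GEE, exchangeable, SD 3.27, 90 per arm, correlation 0.3 and 0.7, 100 trials per scenario:

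| True d1 / d3 / d6 | Formula | Model as written | With visit and arm-by-visit |
|---|---|---|---|
| 1.5 / 0.75 / 0 | 2.25/3 = 0.75 | 0.76 to 0.80 | 1.45–1.54 / 0.78–0.80 / 0.04–0.05 |
| 1.5 / 0 / −1.5 | 0/3 = 0 | 0.01 to 0.05 | 1.45–1.54 / 0.03–0.05 / about −1.45 |
| 0 / 0 / 1.5 | 1.5/3 = 0.5 | 0.51 to 0.55 | −0.05 to 0.04 / 0.03–0.05 / 1.54–1.55 |

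The fuller model recovers each visit's difference within simulation error. The model as written cannot.

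**Step 3: unequal dropout with no true difference.** Under independence weights, each arm's mean is the average of the values observed.

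- ODI-like visit means 45/30/25, 6-month loss 5% against 25%: (45 + 30 + 0.75×25)/2.75 − (45 + 30 + 0.95×25)/2.95 = 34.09 − 33.47 = 0.62 points. A simulated exchangeable GEE gave 0.73, against 0.01 with visit terms.
- NRS-like means 5/4/3.5, loss at 3 and 6 months of 5% and 10% against 15% and 30%: (5 + 0.85×4 + 0.70×3.5)/2.55 − (5 + 0.95×4 + 0.90×3.5)/2.85 = 4.255 − 4.193 = 0.06 points.

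The bias exists but is small in both examples. It grows with the change in means over visits and with the imbalance in loss.

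**Step 4: the price of by-visit estimates.** With residual within-patient correlation r, the ratio of the single-visit to the averaged standard error is √(3/(1 + 2r)). At r = 0.5 this is √1.5 = 1.22. At r = 1/3 it is √1.8 = 1.34. At r = 0.3 it is √1.875 = 1.37. Simulated ratios were 1.22 and 1.33.

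**The case against.** **A by-visit route may already exist.** Change in ODI at 3 months is a continuous between-group comparison, so the rule in SAP 7.2 and Protocol 13.4 could be applied to it. The table shells are in a separate mock-up that is not available here. A reader might infer from 7.9.2 that no visit will get its own estimate, and the documents do not support going that far. What stands is that 7.9.2 is the specific rule for these endpoints, 7.2 is general and tied to no visit, and the SAP does not say which one governs.

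**The visit term may simply have been left out of the sentence.** Mixed models for repeated measures usually carry visit, and 7.9.2 introduces the model by naming the three visits. That is plausible. But the section gives an explicit list and offers GEE first, and 7.9.1.2 shows that the authors list a repeat index when they intend one. The optional confounders do not fill the gap: visit is not a confounder of randomised arm, and a visit main effect alone would still leave one averaged arm effect.

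**The averaged effect can be the more powerful one.** This is correct when the difference is constant over visits. In simulations with a constant 4-point difference, the averaged model rejected in 52.5% of runs against 35% for the 6-month contrast, or 79% against 55% when baseline shared the patient effect. Power comparisons in either direction depend on the assumed pattern, so none is offered as the size of this problem.

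**The trial's conclusion does not depend on it.** This stands. Both primary endpoints have their own 6-month definitions and margins (1.5 for NRS, 2.5 for angle) in SAP 7.9.1, and the secondary endpoints carry no margin or success rule.

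**Conclusion.** The point holds for the continuous secondary endpoints and the model as written in SAP 7.9.2. That model estimates a visit-averaged difference that matches no listed endpoint. A single-visit difference is reduced to about one third, and opposite differences can cancel completely. The one-third figure rests on complete data and equal visit weights, not on any assumed effect size. Bias from unequal dropout is a further, smaller consequence: about 0.6 to 0.7 points on an ODI-like scale and 0.06 on an NRS-like scale, under the assumed means and losses.

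A reader might infer that the non-inferiority claim or the safety reporting is compromised. It is not, because neither uses this model. The matter is one the SAP should correct before analysis, because it decides what the secondary results mean.

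**What to change.** In SAP 7.9.2:

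- Add visit (1 day, 3 months, 6 months) as a categorical factor, and arm-by-visit, to the fixed terms of each model.
- Report the arm difference with its 95% CI at every visit listed for each outcome, without ranking the visits. For NRS, report 1 day and 3 months as the secondary results.
- State that this model, and not the t-test or Mann-Whitney rule in 7.2, governs the continuous secondary endpoints.
- Reconcile with Protocol 5.2.2 whether angle at 6 months is a secondary endpoint.

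The cost is SAP wording and extra model terms, with no new data or patients. Per-visit intervals will be roughly 20% to 35% wider than the averaged one under assumed within-patient correlations of about 0.3 to 0.5. Some power is given up if the true difference is constant over visits.
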